4.2 Clinical Hypothesis

The study skincare products will produce a statistically significant decrease in psoriasis clinical grading scores over the course of 8 weeks of use when compared with baseline scores. Additionally, the study products will be well tolerated by subjects, with no statistically significant increases in scores for tolerability parameters at any study time point when compared to baseline

Protocol GLI.04.US.SL.035

CONFIDENTIAL

scores. Furthermore, the study products will be well perceived by subjects according to analyses of QoL assessment, with a statistically significant improvement in subject response values when compared with baseline, and self-assessment questionnaire, with a statistically significant proportion of favorable responses compared to unfavorable responses.

For the explorable endpoint, the study products will produce a statistically significant improvement in efficacy via imaging analysis values over the course of the study when compare with baseline.

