12. STATISTICAL ANALYSIS

12.1 General

All study data will be listed in subject data listings.

All continuous endpoints will be summarized descriptively including N, mean, median, standard deviation, minimum and maximum values, for the observed value as well as the change from Baseline. Categorical endpoints will be presented in frequency tables with number and percentage of observations for each level.

Confidence intervals will be two-sided and constructed at a confidence level of 95%. Statistical tests will be performed at a significance level of 5%, and *p* values will be two-sided.

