12.4 Statistical Analysis Plan

Mean of the change from Baseline will be estimated at applicable post-Baseline timepoint. The null hypothesis, that the mean change from Baseline is zero, will be tested using methods described in

Table 5.

The following will be calculated and reported for each parameter at applicable post-Baseline timepoint(s):

$$\text{Percent mean change from baseline} = \frac{(\text{visit mean score} - \text{baseline mean score})}{\text{baseline mean score}} \times 100$$

$$\text{Percent of subjects improved/worsened} = \frac{(\text{number of subjects improved/worsened from baseline})}{\text{total number of subjects}} \times 100$$

Protocol Version 02: 29 January 2024

This document contains confidential, proprietary information.

Protocol GLI.04.US.SL.035

CONFIDENTIAL

Table 5. Statistical Analysis Plan

Evaluation	Change from Baseline	Notes/Interpretation
Clinical Grading 
 BSA TLSS PGA 	One-sample t-test; If normality fails, a Wilcoxon signed-rank test will be used.	A decrease in scores indicates an improvement.
Tolerability Grading 
 Dryness Burning/Stinging Itching 	One-sample t-test; If normality fails, a Wilcoxon signed-rank test will be used.	A decrease in scores or lack of significant increase indicates tolerability/safety of the treatment products.
Macroscopic Imaging 
 Skin smoothness Skin roughness 	One-sample t-test; If normality fails, a Wilcoxon signed-rank test will be used.	A decrease in values indicates an improvement in skin smoothness. An increase in values indicates an improvement in roughness.
Capacitance Imaging 
 Homogeneity 	One-sample t-test; If normality fails, a Wilcoxon signed-rank test will be used.	An increase in values indicates a homogeneous moisture distribution.
QoL Questionnaire	Wilcoxon signed-rank test	A decrease in response values indicates an improvement.
Self-Assessment Questionnaire	N/A	Percentage of favorable and unfavorable responses will be provided for each question.

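### Tolerability is concluded from the lack of a significant increase in mean score, which is not evidence of tolerability and ignores subjects who worsen

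*Combined protocol and SAP*

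**What the plan says.** Tolerability shares the primary objective with efficacy (Synopsis; section 4.1). Under section 11.1, dryness is graded by the investigator and burning/stinging and itching by the subject. All are graded on the target lesions, from 0 to 3 with half points allowed, at Baseline and Weeks 2, 4 and 8.

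For these scores section 12.4 sets out a test of no difference: "The null hypothesis, that the mean change from Baseline is zero, will be tested using methods described in" Table 5. The method is "One-sample t-test; If normality fails, a Wilcoxon signed-rank test will be used". Section 12.1 sets a 5% level with two-sided p values, so 2.5% lies in the direction of worsening.

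The interpretation column of Table 5 then reads: "A decrease in scores or lack of significant increase indicates tolerability/safety of the treatment products". Section 4.2 says the products will be well tolerated, "with no statistically significant increases in scores for tolerability parameters at any study time point when compared to baseline".

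The documents give no margin for acceptable worsening, no SD, no power, and no rationale for the 40 to 50 completers in section 6.1. Every subject must be on or starting a prescription psoriasis treatment (sections 6.3 and 6.5.1). Table 5 compares only with baseline.

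**The concern.** Failing to reject zero change is treated as a positive finding of tolerability. That result becomes more likely as the sample shrinks or the scores get noisier, so a weaker study passes more easily.

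The criterion also looks only at the mean. Itching and dryness are features of the disease that the prescription is meant to improve, and they are scored on the same lesions. Improvement in some subjects can therefore offset irritation in others, and with no concurrent comparison in the analysis the two cannot be separated. At stake is whether the tolerability half of the primary objective rests on evidence that worsening was small, or only on the study not having detected any.

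**Working it through.** There is no figure in the plan to reproduce. From the documents: 40 completers (the section 6.1 minimum), two-sided 5%, null of zero mean change. Assumed, because not given: SD of change 0.8 to 1.0 grade, with 0.6 as a lower sensitivity value.

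**Step 1: how often real worsening passes at one visit.** P(no significant increase) is the noncentral t distribution function, n − 1 degrees of freedom and noncentrality d√n/SD, evaluated at t(0.975, n − 1) = 2.023 for n = 40.

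| True mean increase d | SD 0.8 | SD 1.0 |
|---|---|---|
| 0.2 | 0.66 | 0.77 |
| 0.3 | 0.36 | 0.54 |
| 0.5 | 0.03 | 0.13 |

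The largest observed mean increase that stays non-significant is 2.023 × SD/√40, which is 0.256 at SD 0.8 and 0.320 at SD 1.0. The upper 95% limit is then twice that, 0.51 and 0.64 grade, so a passing result can be compatible with an increase of more than half a grade.

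**Step 2: offset by the prescription.** Suppose the product adds 0.4 grade (n = 40, SD 1.0). The rule passes with probability 0.31 if the prescription does nothing, 0.77 if it takes off 0.2 grade, and 0.975 if it takes off 0.4.

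**Step 3: a reacting minority.** Suppose 8 of 40 worsen by one grade, 16 improve by one and 16 do not change.
- Mean = (8 − 16)/40 = −0.2.
- Sum of squares about the mean = 24 − 40 × 0.04 = 22.4, so SD = √(22.4/39) = 0.758 and SE = 0.758/√40 = 0.120.
- t = −0.2/0.120 = −1.67, p = 0.10 (Wilcoxon p also 0.10).

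The rule concludes tolerability although 20% worsened (exact 95% CI 9 to 36%).

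**Step 4: would a margin equal to the 0.5-grade scoring step repair the rule?** The present rule passes when the observed mean is below the CI half-width h. A rule that the upper limit be below 0.5 passes when the mean is below 0.5 − h. The second is stricter only if h exceeds 0.25.

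| n, SD | h | 0.5 − h | Pass at true +0.2: now / margin | Pass at true +0.3: now / margin |
|---|---|---|---|---|
| 40, 0.6 | 0.192 | 0.308 | 0.46 / 0.87 | 0.13 / 0.54 |
| 40, 0.8 | 0.256 | 0.244 | 0.66 / 0.64 | 0.36 / 0.34 |
| 40, 1.0 | 0.320 | 0.180 | 0.77 / 0.46 | 0.54 / 0.23 |
| 50, 0.8 | 0.227 | 0.273 | 0.59 / 0.74 | 0.26 / 0.41 |

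At n = 40 and SD 0.8 the two rules nearly coincide. With less noise, or with 50 completers at that SD, the 0.5-grade rule is the more lenient and can pass a mean increase that is statistically significant. It also passes the Step 3 example, whose upper limit is −0.2 + 2.023 × 0.120 = +0.04.

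**The case against.** The strongest reply is that the plan does not rely on the mean alone. Section 12.4 requires the percent of subjects improved and worsened for each parameter and timepoint. Section 11.2 has clinically relevant unfavourable changes from baseline in protocol parameters reported as adverse events whatever the cause. Section 11.2.2 records as a related adverse event any local reaction that leads to permanent discontinuation or, with stated exceptions, corrective treatment. A reader might infer from Step 3 that a reacting minority would go unseen. The documents do not support that: it would be visible in planned outputs. What stands is that none of these outputs enters the stated criterion.

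Section 4.2 is also stricter than one visit, since it requires "no statistically significant increases in scores for tolerability parameters at any study time point". For one parameter with a sustained increase at SD 0.8 and an assumed between-visit correlation of 0.5, simulation gives a chance of passing all three visits of about 0.4 at 0.2 grade and 0.14 at 0.3. This reduces the leniency but does not turn non-significance into evidence.

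A reader might instead conclude that a harmless product fails 20% of the time: three parameters at three visits give nine tests, and 1 − 0.975^9 = 0.20. That assumes independence, which is implausible for repeated scores on the same subjects. At an assumed common correlation of 0.5 the figure is about 13 to 14%.

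**Conclusion.** The point holds and should be fixed. Treating lack of a significant increase as tolerability is an invalid inference on half of the primary objective. At 40 completers and an SD of 0.8 to 1.0, mean worsening of 0.2 to 0.3 grade passes a given visit with probability between 0.36 and 0.77. The SDs are assumptions, and no figure in the documents is contradicted.

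It would go too far to say that the rule cannot detect harm: a 0.5-grade mean worsening is missed only 3 to 13% of the time under the same assumptions. Nor does a margin by itself cure the problem. A bound on the mean neither exposes a minority who react nor separates the product from the prescription.

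A separate, minor query concerns the macroscopic imaging row of Table 5: "A decrease in values indicates an improvement in skin smoothness. An increase in values indicates an improvement in roughness". This runs opposite to the plain meaning of the names. A reader might infer that worsening texture would be reported as benefit. The documents do not establish this, because section 10.2.2 says only that software calculates the values and does not give their coding. The endpoint is exploratory and measured at Site 2 only.

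**What to change.** 1. Delete the lack-of-significant-increase wording from the tolerability row of Table 5, and the matching clause in section 4.2.
2. For each parameter and visit, conclude on the mean only if the upper limit of the two-sided 95% CI for mean change (the level already set in section 12.1) is below a margin that the sponsor pre-specifies and justifies for a group mean. The 0.5-grade step in section 11.1 is a scoring step for one individual and is not such a justification. Report any statistically significant increase as such, even when the margin is met.
3. Make subject-level worsening part of the tolerability conclusion: the number and percent worsening by at least 1 grade, with an exact 95% CI, for each parameter and visit. This adds a threshold and an interval to a summary already planned.
4. Word the conclusion as tolerability under combined use with prescription treatment.
5. Separately, check the macroscopic imaging row against the software's index coding and correct or explain it.

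These are wording changes, and the data are already collected. The real cost is that the sponsor must commit to a margin, and the sample limits how tight it can be. With no true change and 80% power, completers needed are about (SD × (1.960 + 0.842)/margin)². Over an assumed SD range of 0.6 to 1.2, that is 12 to 46 for a margin of 0.5 and 46 to 181 for 0.25. If the justified margin is tighter than 40 to 50 completers can support, the report should give the interval and draw no conclusion of tolerability on the mean.

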Effectiveness Assessments:	BSA, TLSS, and PSA grading by investigator. Standardized photography of target lesions using digital camera. Macroscopic camera with imaging analysis, and capacitance imaging system (Site 2 only). Treatment satisfaction using QoL and self-assessment questionnaire.
Safety Assessments:	Tolerability assessment by investigator and subject. Adverse Events will be obtained from signs and symptoms reported by the subject or detected during study visit.
Statistical Methods:	In general effectiveness, safety and baseline characteristics variables will be presented using descriptive statistics, and graphs as appropriate. Continuous endpoints will be summarized using descriptive statistics, e.g., mean, median, standard deviation, minimum and maximum values. Categorical endpoints will be presented in frequency tables with number and percentage of observations for each level.

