3. BACKGROUND AND RATIONALE

Psoriasis is a chronic inflammatory skin condition that affects 2% of the population worldwide, and is characterized by the formation of distinct, scaly, erythematous plaques.^{1, 2} These plaques can be painful, pruritic, and disfiguring. Psoriasis can substantially diminish quality of life and negatively affect patient's well-being.² In mild to moderate disease, first-line treatment typically involves topical therapies, such as corticosteroids, vitamin D3 analogues and combination products. Biologic agents have emerged as highly potent treatment options for moderate to severe psoriasis; however, because complete clearance is not always achieved by a biologic agent, most patients who receive biologic therapies continue to use adjunctive topical therapies³.

Skincare products in the treatment of psoriasis have historically been thought to provide only symptomatic relief, but new evidence suggests moisturizers may confer therapeutic benefit by supporting epidermal barrier repair. Patients with psoriasis are advised to moisturize using lipid-replenishing ointments or creams to relieve itching and prevent skin dryness, and as such, frequent application of moisturizers has been standard in the management of psoriasis⁴. Other researchers have noted that moisturizers can confer therapeutic effects in psoriasis⁵. One study involving Cetaphil Moisturizing Cream found that use of moisturizer alone prevented further damage to skin barrier and increased skin hydration⁶. This study is to assess the efficacy of Cetaphil skincare products when used in conjunction with prescription treatment for plaque psoriasis.

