10.1.2. Target Lesion Severity Score (TLSS)

Investigator will perform clinical grading of TLSS, at Baseline, Week 2, 4, and 8. The target lesion parameters will be assessed using the following numerical scales.⁸ Odd scores may be used as necessary to more accurately describe the skin condition.

Table 2. TLSS Grading

Parameter	Score	Definition
Erythema	0	No evidence of erythema
	2	Pink coloration
	4	Red coloration
	6	Very red coloration
	8	Extreme red (deep red) coloration
Induration	0	No evidence of plaque above normal skin level
	2	Slight definite elevation above normal skin level
	4	Moderate elevation above normal skin level
	6	Marked elevation above normal skin level
	8	Very marked elevation above normal skin level
Scaling	0	No evidence of scaling on the lesions
	2	Mild mainly fine scales, some lesions at least partially covered
	4	Moderate somewhat coarser scale, most lesions at least partially covered
	6	Severe coarse thick scales, virtually all lesions covered with rough surface
	8	Very severe coarse very thick scales, all lesions covered with rough surface

TLSS score is calculated as cumulative total of all 3 parameters, which a maximum score of 24 (8 x 3).

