11.1 Tolerability Assessment

Tolerability assessment will be performed by the Investigator (dryness) and by subjects (burning/stinging and itching) using a 4-point analog scale (with half-point scores used as necessary to better describe the clinical condition). Investigator and subjects will grade the degree of irritation of target lesion areas, at Baseline, Week 2, 4, and 8.

Table 4. Tolerability Scales

Score	Grade	Description
Itching: as reported by the subject within the last 24 hours		
0	None	No itching
1	Mild	Slight itching, not really bothersome
2	Moderate	Definite itching that is somewhat bothersome
3	Severe	Intense itching that may interrupt daily activities and/or sleep
Dryness: as assessed by the investigator		
0	None	No dryness
1	Mild	Slight, but definite roughness
2	Moderate	Definite roughness
3	Severe	Marked roughness
Burning/Stinging: as reported by the subject within the last 24 hours		
0	None	No burning
1	Mild	Slight burning sensation; not really bothersome
2	Moderate	Definite warm, burning that is somewhat bothersome
3	Severe	Hot burning sensation that causes definite discomfort and may interrupt daily activities and/or sleep

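### A fall in itching or dryness is read as evidence of product tolerability, although the rationale names both as benefits of moisturizers and the design cannot separate products from prescription

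*Combined protocol and SAP*

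**What the plan says.** Section 3 (Background and Rationale) gives symptom relief as a reason for moisturizing: "Patients with psoriasis are advised to moisturize using lipid-replenishing ointments or creams to relieve itching and prevent skin dryness". It gives other reasons as well: "new evidence suggests moisturizers may confer therapeutic benefit by supporting epidermal barrier repair", and it cites a study of the moisturizing cream that reported increased hydration.

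Section 11.1, under Safety Assessments, collects the symptoms: "Tolerability assessment will be performed by the Investigator (dryness) and by subjects (burning/stinging and itching) using a 4-point analog scale". Half points are allowed, and grading takes place at Baseline and Weeks 2, 4 and 8. The synopsis likewise puts this assessment under safety.

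Section 4.2 states the directional efficacy hypothesis: "The study skincare products will produce a statistically significant decrease in psoriasis clinical grading scores over the course of 8 weeks of use". Table 5 lists clinical grading as BSA, TLSS and PGA. For the tolerability grades, 4.2 expects only the absence of a significant rise at any visit.

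Table 5 (section 12.4) applies the same test to both groups: a one-sample t-test of zero mean change, or Wilcoxon signed-rank if normality fails. It reads the results differently. A fall in BSA, TLSS or PGA is an improvement. For dryness, burning/stinging and itching the note is: "A decrease in scores or lack of significant increase indicates tolerability/safety of the treatment products".

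**The concern.** The same movement in a score is read as improvement for the clinical grades and as safety for itching and dryness, although the rationale presents relief of itch and prevention of dryness as things moisturizers do. Two things follow.

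First, the plan states no benefit hypothesis for these grades. If they fall, any claim of symptom improvement is framed after open-label data have been seen.

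Second, and more serious, the safety reading is not valid. Section 6.5.1 requires a prescription psoriasis treatment, section 6.2 allows it to be newly started, and the analysis is change from baseline with no control. If the prescription improves the disease, itch and dryness fall whether or not the products irritate. The report could then call the products well tolerated on evidence that does not bear on the question.

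**Working it through.** The documents give no power, effect size, SD of change or tolerability margin, so there is no plan figure to reproduce. The check has four parts.

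**Inputs.** 40 to 50 completers (section 6.1). Two-sided tests at 5% (section 12.1). Scale 0-3 with half points (section 11.1). SD of change assumed at 0.6, 0.8 or 1.0 points. Power is for the t-test, from the noncentral t distribution: P(T > t_crit) with n - 1 degrees of freedom and noncentrality d × √n, where d is the mean change divided by the SD of change.

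**1. Would the planned test show a fall?** Yes.
- n = 40: t_crit = 2.023, and 80% power is reached at d = 0.454.
- n = 50: t_crit = 2.010, and 80% power is reached at d = 0.404.
- For a true fall of 0.5 points at n = 40, power is 0.999, 0.97 and 0.87 at SD 0.6, 0.8 and 1.0.

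Section 12.4 also reports percent mean change and percent improved or worsened for each parameter. What is missing is the pre-specified reading, not the analysis.

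**2. Does a significant mean fall exclude worsening?** No. Take an illustrative 40 subjects, 30 falling by 1 point and 10 rising by 1 point.
- Mean change = (-30 + 10)/40 = -0.5.
- Sum of squares about the mean = 30 × 0.5² + 10 × 1.5² = 7.5 + 22.5 = 30, so SD = √(30/39) = 0.877.
- t = -0.5/(0.877/√40) = -3.61, two-sided p = 0.0009 (Wilcoxon p = 0.0016).
- Worsened: 10/40 = 25%, exact 95% confidence interval 13% to 41%.

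Table 5 would read this result as tolerability.

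**3. Is the other half of the rule any better?** No. The probability that a true mean rise of 0.25 points fails to reach significance is 1 - power:

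| SD of change (assumed) | n = 40 | n = 50 |
|---|---|---|
| 0.6 | 0.27 | 0.18 |
| 0.8 | 0.51 | 0.42 |
| 1.0 | 0.66 | 0.59 |

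The two halves also overlap: a mean decrease is itself a lack of significant increase. Deleting only the clause on a decrease would therefore change nothing.

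**4. What does a multiplicity adjustment cost?** With Bonferroni over Week 8 itching and dryness (0.025 each), the detectable fall at 80% power moves from 0.45 to 0.50 SD at n = 40 and from 0.40 to 0.45 SD at n = 50. Testing both at all three follow-up visits would instead raise the efficacy-grading family from 3 × 3 = 9 to 5 × 3 = 15 tests. The familywise error, if the tests were independent (an assumption), would go from 1 - 0.95⁹ = 0.37 to 1 - 0.95¹⁵ = 0.54. This is why one named visit is preferable.

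**The case against.** The strongest reply is that nothing is lost. The two-sided test and the percent improved would reveal a fall, so a reader who infers that the trial cannot show relief from baseline goes too far. That stands: the gap is a label and a directional hypothesis.

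It is also tempting to say that the plan leaves itch and dryness out of efficacy altogether. The documents do not support this. Questionnaires are listed among the efficacy methods in section 10. DLQI item 1 includes itch, and several self-assessment items concern dryness or hydration. These measures are weaker. The DLQI item merges itch with soreness, pain and stinging inside a total score; the self-assessment items have no baseline, and none names itch.

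Nor are itch and dryness the whole rationale. Section 3 also names barrier repair, therapeutic effects and hydration, so testing BSA, TLSS and PGA follows from it. One might go on to argue that the TLSS scaling component should be tested separately because it is nearer to an emollient's action. The plan defines the endpoint as a sum ("TLSS score is calculated as cumulative total of all 3 parameters"). Whether the sub-score or the total has more power depends on whether scaling alone changes or all three components do, and the documents do not settle that. It is a preference.

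Finally, relabelling a fall as efficacy does not make it attributable to the products. That is correct, and it limits what the new outcomes may claim. It does not rescue the safety reading, which has the same confounding.

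**Conclusion.** The concern holds as a mismatch between rationale, hypothesis and interpretation rule, and as an invalid safety inference. The itching and dryness grades have no pre-specified symptom-improvement reading, and the Table 5 note accepts as proof of tolerability either a mean fall that the prescription could produce or a non-significant rise that small numbers could produce.

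On size, the existing test detects a mean fall of 0.45 SD (40 completers) or 0.40 SD (50) with 80% power, so making these grades efficacy outcomes needs no further subjects for effects of that order. Against that, a true mean rise of 0.25 points would go unflagged in 27% to 66% of trials at n = 40. These figures rest on assumed SDs of 0.6 to 1.0 points and on the t-test being used. The 30-versus-10 example is an illustration, not a forecast. The finding about the interpretation rule needs none of these assumptions.

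**What to change.** - **Section 4.2 and Table 5:** list itching and dryness at Week 8 as secondary efficacy outcomes with a hypothesised decrease. State that the result is change from baseline on products plus prescription, without attribution to the products. Give the two outcomes a stated place in a testing order, or adjust for multiplicity (Bonferroni over the two is enough).
- **Table 5 tolerability note:** replace it so that neither a mean decrease nor a non-significant increase counts as proof of safety.
- **Tolerability readout:** base it on burning/stinging and on the percent of subjects worsened from baseline on each of the three scales, with 95% confidence intervals. Section 12.4 already calculates percent worsened. It too is uncontrolled, so it should be reported as what was observed on the combined regimen.

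The cost is protocol and SAP wording, with no new data, visits or subjects. The downside is two more efficacy results to place, a slightly larger detectable effect if Bonferroni is used, and a tolerability statement that will read less favourably than the present rule allows.
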